#### *Immune-mediated hepatitis*

Monitor subjects for changes in liver function (at the start of treatment, periodically during treatment and as indicated based on clinical evaluation) and symptoms of hepatitis, and exclude other causes of hepatitis.

Administer corticosteroids (initial dose of 0.5 – 1.0 mg/kg/day for grade 2 events, and 1 – 2 mg/kg/day for grade 3 or greater events, of prednisone or equivalent, followed by a taper) and, based on severity of liver enzyme elevations, withhold or discontinue pembrolizumab.

#### *Immune-mediated nephritis*

Monitor patients for changes in renal function and exclude other causes of nephritis. Administer corticosteroids for grade 2 or greater events (initial dose of 1 – 2 mg/kg/day prednisone or equivalent, followed by a taper), withhold pembrolizumab for moderate (Grade 2), and permanently discontinue pembrolizumab for severe (Grade 3) or life-threatening (Grade 4) nephritis.

#### *Immune-mediated endocrinopathies*

Monitor subjects for signs and symptoms of hypophysitis (including hypopituitarism and secondary adrenal insufficiency) and exclude other causes of hypophysitis. Administer corticosteroids to treat secondary adrenal insufficiency and other hormone replacement as clinically indicated, withhold pembrolizumab for moderate (Grade 2), withhold or discontinue pembrolizumab for severe (Grade 3) or for life-threatening (Grade 4) hypophysitis.

Monitor subjects for hyperglycemia or other signs and symptoms of type 1 diabetes. Exclude other causes of diabetes. Administer insulin for type 1 diabetes, and withhold pembrolizumab in cases of severe hyperglycemia until metabolic control is achieved.

Thyroid disorders have been reported in subjects receiving pembrolizumab and can occur at any time during treatment; therefore, monitor subjects for changes in thyroid function (at the start of treatment, periodically during treatment and as indicated based on clinical evaluation) and clinical signs and symptoms of thyroid disorders. Hyperthyroidism may be managed symptomatically. Withhold pembrolizumab for severe (Grade 3) hyperthyroidism, and permanently discontinue pembrolizumab for life-threatening (Grade 4) hyperthyroidism. Hypothyroidism may be managed with replacement therapy without treatment interruption and without corticosteroids. For subjects with severe (Grade 3) or life-threatening (Grade 4) endocrinopathy that improves to Grade 2 or lower and is controlled with hormone replacement, continuation of pembrolizumab may be considered.

#### *Other immune-related AEs*

The following additional clinically significant, immune-mediated adverse reactions were reported in less than 1% (unless otherwise indicated) of subjects treated with pembrolizumab: uveitis, myositis, Guillain-Barré syndrome, pancreatitis and severe skin reactions (1.1%).

In addition a set of irAEs have also been classified as immune-related events of clinical interest (irECI) a full list of these can be found in events of clinical interest guidance and Appendix 5. Patients with symptomatic irECIs should immediately stop receiving pembrolizumab and be evaluated to rule out non treatment related causes of the event. Overdose and liver toxicity irECIs irrespective of relationship to the study drug should be reported within 24 hours of the investigator being aware to the Sponsor (via RM-CTU) who will in turn notify MSD. If the irECI is determined to be associated please refer to ECI guidance document and Appendix 5 for the recommendations on the management of these irECIs. If the event is not considered to be associated with the study drug the physician should exercise individual clinical judgment on the event management based on the patient. Any additional questions of the collection or information on management of irECIs should be directed to the Sponsor (via RM-CTU).

## 6.6 Supportive Care Guidelines for Pneumonitis

Patients with symptomatic pneumonitis should immediately stop receiving pembrolizumab and have an evaluation. The evaluation may include bronchoscopy and pulmonary function tests to rule out other causes such as infection. If the patient is determined to have study drug associated pneumonitis, the suggested treatment plan is detailed in Table 11.

**Table 11:** Recommended Approach to Handling Pneumonitis

Study drug associated pneumonitis	Withhold/Discontinue Pembrolizumab?	Supportive Care
Grade 1 (asymptomatic)	No action	Intervention not indicated
Grade 2	Withhold pembrolizumab, may return to treatment if improves to Grade 1 or resolves within 12 weeks Second episode of pneumonitis – discontinue pembrolizumab if upon re-challenge the patient develops a second episode of Grade 2 or higher pneumonitis.	Consider pulmonary consultation with bronchoscopy and biopsy/BAL. Conduct an in person evaluation approximately twice per week Consider frequent Chest X-ray as part of monitoring Treat with systemic corticosteroids at a dose of 1 to 2 mg/kg/day prednisone or equivalent. When symptoms improve to Grade 1 or less, steroid taper should be started and continued over no less than 4 weeks. Consider antibiotics
Grade 3 and Grade 4	Discontinue pembrolizumab	Hospitalise patient Bronchoscopy with biopsy and/or BAL is recommended. Immediately treat with intravenous steroids (methylprednisolone 125 mg IV). When symptoms improve to Grade 1 or less, a high dose oral steroid (prednisone 1 to 2 mg/kg once per day or dexamethasone 4 mg every 4 hours) taper should be started and continued over no less than 4 weeks. If IV steroids followed by high dose oral steroids does not reduce initial symptoms within 48 to 72 hours, treat with additional anti-inflammatory measures. Discontinue additional anti-inflammatory measures upon symptom relief and initiate a prolonged steroid taper over 45 to 60 days. If symptoms worsen during steroid reduction, initiate a re-tapering of steroids starting at a higher dose of 80 or 100mg followed by a more prolonged taper and administer additional anti-inflammatory measures, as needed add prophylactic antibiotics for opportunistic infections. The use of infliximab may be indicated as appropriate.

For Grade 2 pneumonitis that improves to  $\leq$  Grade 1 within 12 weeks, the following rules should apply:

- First episode of pneumonitis: May increase dosing interval by one week in subsequent cycles
- Second episode of pneumonitis: Permanently discontinue pembrolizumab if upon re-challenge the patient develops pneumonitis  $\geq$  Grade 2

## 6.7 Diet/Activity/Other Considerations

### 6.7.1 Diet

Patients should maintain a normal diet unless modifications are required to manage an AE such as diarrhoea, nausea or vomiting.

### 6.7.2 Contraception

Pembrolizumab may have adverse effects on a foetus *in utero*. Furthermore, it is not known if pembrolizumab has transient adverse effects on the composition of sperm. Non-pregnant, non-breast-feeding women may be enrolled if they are willing to use 2 methods of birth control or are considered highly unlikely to conceive. Highly unlikely to conceive is defined as 1) surgically sterilized, or 2) postmenopausal (a woman who is  $\geq$ 45 years of age and has not had menses for greater than 1 year will be considered postmenopausal), or 3) not heterosexually active for the duration of the study. The two birth control methods can be either, two barrier methods or a barrier method plus a hormonal method to prevent pregnancy. Patients should start using birth control from screening throughout the study period up to 120 days after the last dose of study therapy. Male patients with partners of child bearing potential will also be required to agree to use an adequate method of contraception starting with the first dose of study therapy through 120 days after the last dose of study therapy. The following are considered adequate barrier methods of contraception: diaphragm, condom (by the partner), copper intrauterine device, sponge, or spermicide. Appropriate hormonal contraceptives will include any registered and marketed contraceptive agent that contains an oestrogen and/or a progestational agent (including oral, subcutaneous, intrauterine, or intramuscular agents). Patients should be informed that taking the study medication may involve unknown risks to the foetus (unborn baby) if pregnancy were to occur during the study. In order to participate in the study they must adhere to the contraception requirement (described above) for the duration of the study and during the follow-up period. If there is any question that a patient will not reliably comply with the requirements for contraception, that patient should not be entered into the study.

### 6.7.3 Use in Pregnancy

If a patient inadvertently becomes pregnant while on treatment with pembrolizumab, the patient will immediately be removed from the study. The site will contact the patient at least monthly and document the patient's status until the pregnancy has been completed or terminated. The outcome of the pregnancy will

be reported to the Sponsor and to MSD without delay and within 24 hours if the outcome is a serious adverse experience (e.g., death, abortion, congenital anomaly, or other disabling or life-threatening complication to the mother or newborn). The study investigator will make every effort to obtain permission to follow the outcome of the pregnancy and report the condition of the foetus or newborn to the Sponsor (via RM-CTU) without delay and within 24 hours. If a male patient impregnates his female partner the study personnel at the site must be informed immediately and the pregnancy reported to the RM-CTU and followed as described above and in Section 7.

#### **6.7.4 Use in Nursing Women**

It is unknown whether pembrolizumab is excreted in human milk. Since many drugs are excreted in human milk, and because of the potential for serious adverse reactions in the nursing infant, patients who are breast-feeding are not eligible for enrolment.

#### **6.7.5 Treatment of Overdose of IMP**

For purposes of this trial, an overdose will be defined as any dose exceeding the prescribed dose for pembrolizumab by 20% over the prescribed dose. Please see section 7 for definitions and reporting procedures.

### **6.8 Permanent Discontinuation of Trial Medication and Withdrawal from the Study**

#### **6.8.1 Permanent Discontinuation of Trial Medication**

A patient may be permanently discontinued from the trial medication for any of the following reasons:

- The subject withdraws consent.
- Confirmed radiographic disease progression, please see Section 6.3.11.4.

*Note:* For unconfirmed radiographic disease progression. A patient may be granted an exception to continue on treatment with confirmed radiographic progression if clinically stable or clinically improved.

- Unacceptable adverse experiences
- Intercurrent illness that prevents further administration of treatment
- The patient has a confirmed positive serum pregnancy test
- Noncompliance with trial treatment or procedure requirements
- Administrative reasons
- Completion of 24 months of pembrolizumab

Trial patients will not be enrolled more than once. The primary reason for discontinuation should be recorded on the CRF. Once the trial medication has been discontinued the patient should complete the end of treatment (if applicable) and safety follow-up visit procedures as listed in the schedule of study

assessment (Table 3). After the end of treatment, patients will continue to be assessed for AE and SAE monitoring until completion of the safety follow up visit.

Follow-up actions for patient discontinuing the trial are as follows:

- All patients will be required to:
  - Attend a safety follow-up 30 days after their last dose of pembrolizumab,
- If a patient **progresses or begins a new anti-cancer treatment** they will be required to:
  - Undertake survival status assessments every 12 weeks until death, withdrawal of consent, lost to follow up or the end of the study.
- If a patient discontinues for reasons other than progression during treatment and **does not withdraw their consent to follow up** they will be required to:
  - Attend follow-up assessments every 9 weeks until disease progression, initiation of a new anti-cancer treatment death, end of the study. Information regarding post-study anti-cancer treatment will be collected if new treatment is initiated.

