### **5.3.11.3 Confirmation of Disease Response**

Per RECIST v1.1 & irRC (Appendix 6 & 7), response should be confirmed by a repeat radiographic assessment no less than 4 weeks from the date the response was first documented. The scan for confirmation of response may be performed at the earliest 4 weeks after the first indication of response, or at the next scheduled scan, whichever is clinically indicated.

Immunotherapeutic agents may produce anti-tumour effects by potentiating endogenous cancer-specific immune responses. The response patterns seen with such an approach may extend beyond the typical time course of responses seen with cytotoxic agents and can manifest a clinical response after an initial increase in tumour burden or even the appearance of new lesions. Therefore standard RECIST v1.1 may not provide an accurate response assessment of immunotherapeutic agents such as pembrolizumab.

Therefore, RECIST v1.1 will be used with the following adaptations:

- If radiologic imaging shows initial progressive disease (PD), tumour assessment should be repeated  $\geq 4$  weeks later in order to confirm PD with the option of continuing treatment while awaiting radiologic confirmation of progression.
  - Patients may continue treatment while waiting for confirmation of PD if they are clinically stable as defined by the following criteria:
    - Absence of signs and symptoms indicating disease progression
    - No decline in ECOG performance status
    - Absence of rapid progression of disease
    - Absence of progressive tumour at critical anatomical sites requiring urgent alternative medical intervention. When feasible, patients should not be discontinued until progression is confirmed. This allowance to continue treatment despite initial radiologic progression takes into account the observation that some patients can have a transient tumour flare in the first few months after the start of immunotherapy, but with subsequent disease response. Patients that are deemed clinically unstable are not required to have repeat imaging for confirmation of progressive disease.

- If repeat imaging shows a reduction in the tumour burden compared to the initial scan demonstrating PD, treatment may be continued /resumed.
- If repeat imaging confirms progressive disease, patients will be discontinued from study therapy.

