  - NOTE: If a patient with confirmed radiographic progression (i.e. 2 scans at least 28 days apart demonstrating progressive disease) is clinically stable or clinically improved, and there is no further increase in the tumour dimensions at the confirmatory scan, an exception may be considered to continue treatment upon consultation with the Sponsor. Clinically stable patients should also have at the confirmatory scan no further increase in the target lesions, no unequivocal increase in non-target lesions, and no additional new lesions develop (non-worsening PD) to continue study treatment.

In determining whether or not the tumour burden has increased or decreased, investigators should consider all target lesions as well as non-target lesions.

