#### **5.3.11.4 Confirmation of Disease Progression**

Disease progression should be confirmed at least 4 weeks after the first scan indicating progressive disease in clinically stable patients. Patients who have unconfirmed disease progression may continue on treatment until progression is confirmed.

Clinically stable is defined by one or more of the following criteria:

- Absence of signs and symptoms indicating disease progression
- No decline in ECOG performance status
- Absence of rapid progression of disease
- Absence of progressive tumour at critical anatomical sites (e.g., cord compression) requiring urgent alternative medical intervention

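### Section 6.8.1 allows an exception to stopping pembrolizumab after confirmed progression without the scan conditions that 5.3.11.3 requires

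*Combined protocol and SAP*

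**What the plan says.** Section 5.3.11.3 gives the default rule: "If repeat imaging confirms progressive disease, patients will be discontinued from study therapy". A note beneath it allows one exception. The patient must be clinically stable or improved, "and there is no further increase in the tumour dimensions at the confirmatory scan, an exception may be considered to continue treatment", and the Sponsor must be consulted. For clinically stable patients the confirmatory scan must also show no further target-lesion increase and no unequivocal non-target increase, and there must be "no additional new lesions develop (non-worsening PD) to continue study treatment".

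Section 6.8.1 lists reasons for which trial medication may be permanently discontinued. One entry is "Confirmed radiographic disease progression, please see Section 6.3.11.4". The note under it opens with an unfinished phrase about unconfirmed progression and then gives a rule for confirmed progression: "A patient may be granted an exception to continue on treatment with confirmed radiographic progression if clinically stable or clinically improved".

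Section 5.3.11.4 deals with the interval before confirmation: "Patients who have unconfirmed disease progression may continue on treatment until progression is confirmed". It adds: "Clinically stable is defined by one or more of the following criteria". The four criteria are absence of signs and symptoms of progression, no ECOG decline, absence of rapid progression, and no progressive tumour at a critical site needing urgent intervention. Section 5.3.11.3 lists the same four but introduces them differently: "Patients may continue treatment while waiting for confirmation of PD if they are clinically stable as defined by the following criteria".

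Section 5.1 requires any treatment beyond progression to be discussed with the study sponsor and MSD.

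**The concern.** This is a rule for stopping drug in patients whose disease is worsening, and two sections set different conditions for the same exception. The looser version is in the section on discontinuation, where site staff are likely to look. Its cross-reference does not lead to the stricter version.

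The clinical condition that remains in 6.8.1 is also weak if 5.3.11.4 supplies its meaning. Under the one-or-more wording, a patient with rapid progression, or with progression at a critical site such as cord compression, counts as clinically stable if, for example, ECOG status is unchanged.

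At stake are further pembrolizumab in a patient with growing disease, continued time in a treatment phase where 6.3.1 prohibits other systemic anti-cancer therapy, and a longer late-toxicity window for that patient. If confirmation falls early enough, whether the patient counts as DLT-evaluable may also be at stake.

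**Working it through.** The plan states no figure to reproduce. The check compares the rules and then dates the consequences.

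**1. Conditions for continuing after confirmed progression**

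| Condition | 5.3.11.3 | 6.8.1 |
|---|---|---|
| Clinically stable or improved | required | required |
| No further increase at confirmatory scan | required | not stated |
| No unequivocal non-target increase, no additional new lesions (stable patients) | required | not stated |
| Sponsor consulted | required | not stated (5.1 covers it) |
| If conditions are not met | must stop | not stated |

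**2. Illustrative patient (hypothetical measurements)**

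- Nadir sum 50 mm, first progression scan 60 mm. 60/50 = +20%, and the absolute increase of 10 mm exceeds 5 mm, so this is progression under Appendix 6.
- Confirmatory scan 66 mm. 66/60 = +10% since the progression scan; 66/50 = +32% from nadir.
- ECOG unchanged, no new symptoms.

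Under 5.3.11.3 the further increase rules out the exception and treatment stops. Under 6.8.1 the only stated condition is met and an exception may be granted.

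**3. Calendar**

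With C1D1 as day 1 and 21-day cycles, cycle k starts on day 1 + 21(k − 1): C5D1 = 85, C6D1 = 106, C7D1 = 127, C8D1 = 148.

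The last SBRT fraction is C1D19, day 19. The DLT period ends at 19 + 84 = day 103 by the 12-week wording in 3.2. The same section equates that with C6D1, day 106. By the 3-month wording in 3.2.1 it ends at about 19 + 91 = day 110.

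The date of the first on-study CT can be read two ways:

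- **Reading A, Table 3 columns.** The first CT shares a column with the third research blood sample, which 5.3.13 dates to C5D1. That is day 85 (78–92 with ±7 days). Confirmation at the 4-week minimum is day 113 (106–120). The next CT is 85 + 63 = day 148.
- **Reading B, 5.3.11.2 and Table 3 footnote 1.** Nine weeks counted from C1D1 gives 1 + 63 = day 64 (57–71). Confirmation is day 92 (85–99). The next CT is 64 + 63 = day 127.

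**4. Extra drug up to the next CT**, assuming dosing continued while confirmation was awaited

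- Reading A: last dose without an exception is day 106. An exception adds day 127, and day 148 if that day's dose is given.
- Reading B: last dose without an exception is day 85. An exception adds day 106, and day 127 if that day's dose is given.

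Both give 1 × 200 = 200 mg or 2 × 200 = 400 mg. The late-toxicity window in 2.2.2 closes 28 days after the last dose, so its end moves by 21 or 42 days.

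**5. DLT evaluability**

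Section 4.3 makes a patient who discontinues the trial for progression within 3 months of the last radiotherapy dose non-evaluable for DLTs, to be replaced.

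- Reading A: confirmation on days 106–120 is mostly after the DLT period, although the early end reaches day 106 and precedes about day 110.
- Reading B: confirmation on days 85–99 lies inside the period on every definition of its end.

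On Reading B, if stopping for progression is treated as discontinuing the trial, the choice of rule could decide whether the patient is evaluable or replaced.

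**The case against.** The strongest reply is that 6.8.1 is a summary and 5.3.11.3 is the operative text. The 6.8.1 wording is permissive and compels nothing, and a site that applies 5.3.11.3 complies with both. The wrong cross-reference is evidently meant for 5.3.11.4, which directly follows the full exception. Section 5.1 prevents a site from using the looser wording alone.

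Most of this stands as a limit on the size of the problem. It does not remove the contradiction. Nothing in 6.8.1 says it abbreviates 5.3.11.3. The evident target covers continuation only until confirmation and sets no condition on the scan result. Section 5.1 settles who is consulted but gives no imaging criterion, so the sponsor and MSD would be deciding with two rules in front of them.

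A second reply is that 5.3.11.3 never says all four stability criteria must hold. That is correct, though a list introduced as a definition reads most naturally as joint, and 5.3.11.4 expressly says otherwise.

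A third is that adverse events are recorded to the 30-day safety visit, so extra exposure is still monitored. That is also correct; it does not settle who should receive the extra exposure.

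**Conclusion.** The text is wrong as written: it is an internal contradiction in a stopping rule, and it should be corrected. Its size is per patient, roughly one or two extra 200 mg doses and 21 to 42 more days in the late-toxicity window up to the next CT. This assumes on-schedule dosing while confirmation is awaited and an exception lasting only to that CT. The documents give no basis for a number of patients.

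Three stronger inferences are not supported:

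- A reader might infer that 6.8.1 entitles a progressing patient to continue, or lets a site decide alone. The note says only that an exception may be granted, and 5.1 still applies.
- A reader might infer that DLT assessment is certainly compromised, or certainly untouched. Neither follows. The answer turns on the first CT date, which the documents allow to be read as day 64 or day 85, and on whether stopping drug for progression counts as discontinuing the trial under 4.3.
- A reader might infer that PFS is distorted. The PFS event in 8.1.2 is radiological or clinical evidence of progression, or death, and does not depend on whether drug continues.

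**What to change.** 1. Reword the 6.8.1 note to this effect: *after confirmed radiographic progression, pembrolizumab may continue only if every condition in the 5.3.11.3 note is met, and after the discussion with the sponsor and MSD under 5.1; otherwise it is stopped.*
2. Delete the unfinished opening phrase about unconfirmed progression.
3. Correct the cross-reference to 5.3.11.3 and 5.3.11.4.
4. In 5.3.11.4, replace the one-or-more wording with a requirement that all four criteria hold, so that it matches the list in 5.3.11.3.

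The cost is a wording amendment through the approvals in 9.2 and 10.7: SRC agreement, Sponsor approval, ethics review, and MHRA where required. It needs no extra patients, procedures, data items or analyses.
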